As described above, the FACT-L v.4 contains four general and one lung cancer symptom-specific subscales. General subscales include: Physical Well-Being (PWB), Social/family Well-Being (SWB), Emotional Well-Being (EWB), and Functional Well-Being (FWB).(49) The Lung Cancer Subscale (LCS) assesses symptoms commonly reported by lung cancer patients (e.g., shortness of breath; loss of weight; tightness in chest). The Trial Outcome Index (TOI) is derived by adding scores on the PWB and FWB subscales to the LCS. Because they contain the most relevant questions about symptoms and physical functioning, the LCS and TOI were selected as the primary focus of this analysis. All FACT-L questions are rated on five-point Likert-type scales ranging from 0 (“not at all”) to 4 (“very much”). Therefore, because the seven-items PWB, FWB, and LCS subscales scores range from 0–28 for each subscale, TOI scores range from 0–84. Higher scores represent better QoL or fewer symptoms. The primary outcome is the change in the score on the TOI from baseline to 12 weeks. We estimated that with 120 patients (Figure 7), the study would have 80% power with a two-sided α of 0.05 to detect a significant between-group difference of 6 points in the change in the TOI score from baseline to 12 weeks, given a pooled standard deviation of 11.54 and change in the reference group score of 53.(50) After accounting for 30% attrition rate, the expected number of enrolled patients is 156 allocated 1:1 between LuCApp and usual care groups. This sample size will also allow the detection with 80% power with a two-sided α of 0.05 of 2-points difference in the LCS subscale, assuming

a pooled standard deviation of 4.15 and change in the reference group score of 19.3 (50) (Figure 8). The clinically meaningful changes on the TOI and LCS subscales of FACT-L were derived from Cella et al.(51)

The FACT-L questionnaire will be administered electronically (via LuCApp) or via paper in the control group at baseline, 12 weeks and 24 weeks, with an understanding that in the routine care setting, lung cancer therapies administration intervals vary between patients.

Figure 7 - Sample size estimation: 5 to 10 -point difference in change in TOI score at 12 weeks

[figure not shown]
[figure not shown]
[figure not shown]

Figure 8 - Sample size estimation: 1 to 5-point difference in change in LCS score at 12 weeks

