Assuming a constant recruitment rate of 6 patients per week (2 patients per centre) the study is planned to recruit consecutively for 26 weeks (Figure 9).

Figure 9 - Planned recruitment process

Randomization

Randomization services will be provided by AdvicePharma via a computer system using randomly permuted blocks and stratified by trial centers and therapy (i.e.

chemotherapy, immunotherapy and biological therapy). Nurses or physicians involved in the study will take care of the enrollment phase. After signature of informed consent, a randomization code will be generated electronically and assigned to the patient. During the informed consent procedure, the team will go carefully through the different aspects of the study design and will present LuCApp as well as the usual care alternative. During this phase the patient will have an opportunity to discuss her level of experience with mobile technology.

The study is nonblinded, in fact it is not possible to blind the participants when this type of intervention and these outcomes are under investigation.

Participants will remain on study until discontinuation of cancer treatment, voluntary withdrawal, study termination or death.

Statistical methods

The baseline differences between the intervention and control groups will be assessed using the chi-square (χ^2) test for binary demographic data and the independent sample t-test for continuous variables. We will summarize graphically and numerically the distributions of symptoms, outcomes as well as covariates.

For the primary quality of life endpoint, two groups t-test will be used to compare changes from baseline in FACT-L in the experimental group and the control group 12 weeks after randomization. A multivariable linear regression model, with change score as the dependent variable, adjusted for covariates will be fitted. The proportion of patients in each arm who experienced improved, unchanged, or worsened scores from baseline will be compared using χ^2 or Fisher's exact test. This analysis will be run for both any change and clinically meaningful changes for specific subscales (51). The analyses will be repeated at 24 weeks after randomization.

For all other questionnaires, changes from baseline in the LuCApp group and the control group at 12 and 24 weeks after randomization will be computed using t-test comparison. The SCNS-SF34, usability and ZBI data results will be summarized graphically and numerically.

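### Enrolment of 156 is 120 × 1.30, not 120 / 0.70: with 30% loss by week 12 about 109 patients are evaluable and TOI power is about 77%; the 80% LCS claim fails even at 120 evaluable

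*Combined protocol and SAP*

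**What the plan says.** All of this is in the Combined protocol and SAP, under Methods.

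- **Endpoint** (Sample size): "The primary outcome is the change in the score on the TOI from baseline to 12 weeks".
- **TOI power** (Sample size): "We estimated that with 120 patients (Figure 7), the study would have 80% power with a two-sided α of 0.05", for a 6-point between-group difference and a pooled SD of 11.54.
- **Attrition** (Sample size): "After accounting for 30% attrition rate, the expected number of enrolled patients is 156 allocated 1:1 between LuCApp and usual care groups". No time point is attached to the 30%.
- **LCS power** (Sample size): "This sample size will also allow the detection with 80% power with a two-sided α of 0.05 of 2-points difference in the LCS subscale". The inputs given for this are an SD of 4.15 and a reference-group figure of 19.3. The same section names LCS and TOI together as the main focus of the analysis.
- **Recruitment** (end of Sample size): "Assuming a constant recruitment rate of 6 patients per week (2 patients per centre) the study is planned to recruit consecutively for 26 weeks". Six per week for 26 weeks is 156, so 156 is not a typing slip.
- **Leaving the study** (Randomization): "Participants will remain on study until discontinuation of cancer treatment, voluntary withdrawal, study termination or death".
- **Primary test** (Statistical methods): "two groups t-test will be used to compare changes from baseline in FACT-L" between the arms at 12 weeks. Imputation appears only as a set of sensitivity analyses.

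**The concern.** Attrition is a fraction of those enrolled, so the number required must be divided by the fraction retained. Multiplying by 1.30 instead gives an enrolment that falls below 120 once 30% have left. The primary comparison would then have less than its stated power.

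The LCS statement is a separate problem. Its standardised difference (2 / 4.15 = 0.48) is smaller than that for TOI (6 / 11.54 = 0.52), yet it is claimed to reach the same power at a sample size derived for TOI. A reader who relied on the 80% would give a null LCS result more weight than it deserves.

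**Working it through.** **Inputs, all from Sample size.** Two-sided α 0.05, power 80%, 1:1 allocation. TOI: difference 6, SD 11.54. LCS: difference 2, SD 4.15. Attrition 30%, enrolment 156. The test is the two-sample t-test named in Statistical methods. Both SDs are taken as SDs of change, as the plan uses them.

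**1. Reproduce the 120.** The normal approximation is n per arm = 2(z₀.₉₇₅ + z₀.₈₀)² SD² / Δ² = 2 × (1.960 + 0.842)² × 11.54² / 6² = 58.1, so 59. The exact t-test gives 59.05, so 60 per arm and 120 in total. Power at 120 is 80.6%. The plan's figure stands.

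**2. Check the inflation.**

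- 120 × 1.30 = 156, the plan's figure.
- 120 / (1 − 0.30) = 171.4, so 172.
- 156 × 0.70 = 109.2, so about 109 evaluable.
- 156 leaves 120 only if the loss is at most 36 / 156 = 23.1%.

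**3. Check the LCS requirement.** The normal approximation gives 2 × (1.960 + 0.842)² × 4.15² / 2² = 67.6 per arm, so 68. The t-test gives 68.56, so 69 per arm and 138 evaluable. With 156 enrolled, that allows a loss of at most 1 − 138/156 = 11.5%.

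**4. Power by number evaluable at week 12 (t-test).**

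| Evaluable | How it arises from 156 | TOI power, Δ = 6 | LCS power, Δ = 2 |
|---|---|---|---|
| 109 | 30% lost by week 12 | 76.7% | 70.3% |
| 120 | 23.1% lost | 80.6% | 74.5% |
| 130 | 30% lost by week 24 at a constant rate | 83.7% | 77.8% |
| 138 | 11.5% lost | 85.8% | just over 80% |
| 156 | no loss | 89.7% | 84.9% |

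The 130 row rests on an assumption, since the plan gives no loss curve: week-12 loss is 1 − √0.70 = 16.3%, and 156 × 0.837 = 130.5.

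**5. Differences detectable with 80% power.** TOI: 5.95 points at 120 evaluable and 6.25 at 109. LCS: 2.14 points at 120 and 2.25 at 109.

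**6. Sensitivity to the type of SD.** The plan calls 53 (TOI) and 19.3 (LCS) reference-group changes, although the scales run 0–84 and 0–28. They look like score levels, so the SDs may be SDs of scores. In that case SD of change = SD × √(2(1 − ρ)), where ρ is the baseline to week-12 correlation. For assumed ρ of 0.3, 0.5 and 0.7, the TOI SD of change is 13.65, 11.54 and 8.94, and TOI power at 109 is about 62%, 77% and 93%.

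**The case against.** The strongest reply is that the 30% is undated. The trial lasts 24 weeks, so 30% could be whole-study loss. At a constant rate TOI power is then about 84% and the primary claim holds. That stands, and it makes the TOI shortfall conditional. However, the attrition sentence directly follows a 12-week power calculation, so the week-12 reading is at least as natural. Patients also leave the study when cancer treatment stops, so early loss is a real possibility.

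Second, the sample size in the LCS sentence may mean the 156 just mentioned, where LCS power is about 85%. That requires every enrolled patient to be evaluable, which contradicts the 30% in the sentence before. If loss came late enough for week-12 loss to be 11.5% or less, the LCS claim would hold, but the plan says nothing to support this. Figure 8, cited for this calculation, is not available in the text reviewed, so the number it used cannot be checked.

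Third, doubt about the SDs moves power far more than a 3-point shortfall does. That is true. It is a reason to confirm the SDs, not to leave the arithmetic as it is.

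Finally, this is called a feasibility trial and a pilot. That limits the consequence, but the protocol still makes formal 80% power claims and tests at the 5% level.

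**Conclusion.** The concern holds. The enrolment figure does not follow from 120 evaluable patients and 30% attrition; 172 does. If the 30% is lost by week 12, TOI power is about 77%, roughly 3 points below the claim. If it is the 24-week loss at a constant rate, TOI power is about 84% and the claim is met.

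The LCS claim does not follow from its own inputs at 120 evaluable (about 74%). It falls short at 109 (about 70%) and under the constant-rate 24-week reading (about 78%). All these figures take 11.54 and 4.15 as SDs of change.

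The practical effect is modest and does not call the design into question, but the statements should be corrected.

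**What to change.** Keep 156 and amend the Sample size section:

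1. State whether the 30% applies at week 12 or week 24. If week 24, give the week-12 loss assumed.
2. Replace the two power statements. For the week-12 reading, for example:

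> With 30% attrition by week 12, about 109 of 156 patients will be evaluable, giving about 77% power for a 6-point TOI difference under the assumed SD of change of 11.54. The 120 evaluable patients needed for 80% power are retained only if week-12 attrition is about 23% or less. For a 2-point LCS difference under the assumed SD of change of 4.15, power is about 70% with 109 evaluable and about 74% with 120; 80% power needs 69 evaluable per arm.

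3. Confirm that 11.54 and 4.15 are SDs of change. If they are SDs of scores, state the correlation assumed and recompute.

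The cost is a few sentences, with no added patients, visits or analyses; the stated power becomes less favourable. If the sponsor would rather keep 80% TOI power with 30% loss by week 12, enrolment is 172, which takes 172 / 6 = 28.7, or about 29 weeks instead of 26. LCS power would still be only about 74%.

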
• over 18 years of age individuals of both sexes;• diagnosed with small or non-small cell lung cancer;• patients eligible for chemotherapy, immunotherapy or biological therapy;• patients diagnosed with non-resectable tumor and eligible for neoadjuvant therapies;• life expectancy of six months or more;• a performance status between 0 (asymptomatic) and 2 (symptomatic, <50% in bed during the day) according to the Eastern Cooperative Oncology Group (ECOG) score;• patients fluently speaking Italian;• patients able to provide informed consent to participate in the study;• patients who own a smartphone that can access either the iOS or the Android platform.	
• individuals unable to provide written informed consent;• individuals unable to see the App and all other materials (i.e. are blind);• patients receiving or that plan to receive radiotherapy or surgical resection;• patients already included or about to join other clinical trials;• patients already using other smartphone applications to self-manage cancer symptoms.

Once eligibility has been established, patients will be asked to join the study by the medical oncologists after diagnosis and a face-to-face assessment at the participating centers. Patients will receive an invitation letter, the study leaflet and the informed consent form. This will not be a purely web-based trial, since face-to-face components will still be present: data will be collected through questionnaires via the app for the intervention patients, while standard-of-care patients will complete paper questionnaires during clinic visits, or at home (having received paper questionnaires during the previous visit) or via telephonic interviews with the research team. Outcomes will be self-assessed through Patient Reported Outcome Measures (PROMs) (for further information, please look at the “Outcomes” section) at different points in time. Patients assigned to the intervention arm will be trained to use LuCApp (study staff will provide them with a 15-minute presentation on how to use the App) and will be assisted during the whole study period by a “helpdesk”.

University and participating centers affiliations will be displayed on the invitation letter to obtain participants’ trust but no bias is expected to result from the display of such information.

Intervention (LuCApp)

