The study was developed in close cooperation with an Advisory Board, composed of the Scientific Directors and some healthcare professionals of all participating centers, the researchers at Università Bocconi and representatives of the CRO. Healthcare professionals will be trained on several aspects of the study protocol and on the use of LuCApp before the study begins. A research coordinator from each center will be identified.

Data will be collected through an electronic data capture (EDC), ICE (Integrated Clinical Trial Environment) owned by Advice Pharma Group. This system is compliant with Title 21, Part 11 of the Code of Federal Regulations and with the EU GMP Annex 11 about electronic records for patients. Figure 2 and Figure 3 show the ICE data collection mask and the mobile app (“LuCApp”) data collection mask respectively. Data will be anonymized and stored in a secure database for the study.

Figure 2 - Integrated Clinical Trial Environment mask

[figure not shown]
[figure not shown]

Figure 3 - LuCApp interface

After informed consent and randomization, happening in hospital setting before the start of medical therapy for lung cancer, clinicians will access a secured web-based platform where they will register patients and their credentials. Clinicians will use a hospital PC or their own mobile device connected to internet. Upon activation of a

personal account, patients, with the help of the team, will download the app on their mobiles and log in by inserting their e-mail address and a self-chosen password. For the duration of the trial, the interaction with LuCApp will thus occur via the patient's own mobile and rely on the usual network connectivity. Patients will be required to log in whenever they access the application: this will guarantee that validated data are included in the eCRF and that only patients can access to sensitive data. Patients will not be paid any cash or in-kind amount nor will they be asked to disburse any amount, as LuCApp will be free to download for them.

The intervention presents several different and unique functionalities and components that were designed to aid symptom self-reporting and management. The intervention content is organized as follows:

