- 2) “Temperature” and “Weight” – Patients in the intervention arm will be asked to enter their body temperature everyday and to report their weight once per week (again via mobile banners or emails). Whenever body temperature exceeds the 38 degree Celsius threshold or a 5-percentage point reduction in body weight in the previous two weeks is reported, specific alerts will be generated to inform the clinical team in charge.
- 3) “Tip of the day” – Whenever a patient logs into the app, this feature of the app shows a daily tip, a short suggestion to better manage the side effects of the therapies. The tip is selected randomly among those related to the therapy the patient is undergoing. Tips were drawn from clinical practice guidelines and discussed by a consensus group of experts including medical oncologists, radiation oncologists, surgeons, nutritionists, speech language pathologists, infectious disease specialists, dentists and nurses (18, 19). All tips were later validated with the healthcare professionals from the three sites participating in the trial (final list is available as an attachment “4.1_LuCApp_Annex 1_Tips of the day”).
- 4) “Questionnaires” – A final section allows patients to fill-in several PROMs about their HRQoL and experience with supportive care needs and LuCApp: EuroQol 5D, Functional Assessment of Cancer Therapy (Lung), Hospital Anxiety and Depression scale, supportive care needs survey, usability and satisfaction with the app (see next section on outcomes). Data will be collected at several points in time, depending on the type of questionnaire considered (see next section on outcomes). Questionnaire completion is instrumental in evaluating several end-points and in determining whether LuCApp can improve patient-relevant outcomes compared to

the standard of care. To enable the comparison, patients in the standard of care arm will fill out the same questionnaires via paper at clinic visits or follow up.

[figure not shown]
- 5) “Trend” – In the Trend component, available in the healthcare professional App only, clinicians can access the longitudinal trend of their patients’ clinical parameters. Side effects, temperature and weight are displayed in charts, and it is possible to select a specific timeframe. Clinicians can access the same graphs remotely and analyze the progress of each patient’s clinical parameters and side effects over time (Figure 4).

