of care arm ones, to ensure that behaviors and results will not be influenced. The research teams are also advised not to share feedback or comments for the duration of the trial in order to reduce performance bias as much as possible. Clinicians will receive alerts on their dedicated LuCApp device and will be responsible for managing them in a timely way. A single alert will be generated for each patient and clinical parameter monitored (i.e. temperature, weight, side effects). Healthcare professionals will then be able to gain more information on the symptoms that triggered the alert and to monitor the longitudinal trend of side effects both on their device and on the LuCApp website from a PC or laptop. Professionals will be able to access all other patient information on the secure LuCApp website, only. In response to an alert triggered for a specific patient, clinicians will be requested to act within 24 hours and to document the type of intervention performed among a list of possible alternatives derived from the literature: referral to the ER/hospital, telephone counselling about symptom management, dose modification, supportive medication initiation/change, visit anticipation (13).

To guarantee a greater use of the application automated reminders will be sent to participants both via email and via push notification. Participants will be prompted, via an automated message to update their body temperature and their weight and to fill out the side effects questionnaires. Three rounds of alerts will be generated at 12, 6 and 9 p.m. on the dates when the input of the relative data is scheduled (daily for body temperature, weekly for weight and every three days for the side effects questionnaire, see above).

Both groups will have access to treatment as usual. However, additional training will be provided to intervention arm participants right after enrolment: LuCApp features will be better detailed and training sessions will be scheduled accordingly. Furthermore, during the trial, a support center (“helpdesk”) will be available to help participants with any technical issues that may occur.

Standard of care

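### As the text reads, LuCApp patients answer the baseline FACT-L in an app they receive only after randomisation, and no readable text puts baseline before allocation in either arm

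*Combined protocol and SAP*

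**What the plan says.** Mode and time points are given together in the Sample size section: "The FACT-L questionnaire will be administered electronically (via LuCApp) or via paper in the control group at baseline, 12 weeks and 24 weeks". The Participants section sets the general rule that "data will be collected through questionnaires via the app for the intervention patients" and makes no exception for baseline.

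The order of events is in two places. Under Randomization: "After signature of informed consent, a randomization code will be generated electronically and assigned to the patient". Under Intervention (LuCApp), the step at which clinicians register patients on the web platform is introduced with "After informed consent and randomization, happening in hospital setting before the start of medical therapy for lung cancer"; once a personal account is active, "patients, with the help of the team, will download the app on their mobiles".

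Three further statements bear on what a LuCApp patient meets on opening the app: "Patients will be required to log in whenever they access the application"; "Whenever a patient logs into the app, this feature of the app shows a daily tip"; and "additional training will be provided to intervention arm participants right after enrolment".

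The Outcomes section lists a baseline administration for EQ-5D-5L, FACT-L and HADS without saying whether it precedes or follows allocation. The Standard of care section gives control patients the same schedule, on paper or by telephone. The Randomization section states that the study is not blinded. The primary outcome is the change in TOI from baseline to 12 weeks, compared between arms by a two-group t-test.

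**The concern.** Baseline should be a measurement that allocation cannot have influenced. Here the mode of the baseline questionnaire depends on the arm, and the arm is not known until the code is generated. A LuCApp patient who follows the text learns the allocation, receives the app and then reports baseline quality of life in it. By then the patient may also have logged in, seen a tip on managing side effects and had the app training.

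The outcome is self-reported and the analysis subtracts the baseline. Anything that moves the LuCApp baseline and has faded by week 12 therefore goes straight into the between-arm difference, with the opposite sign. The responder comparison (improved, unchanged or worsened from baseline) uses the same baseline. In an open-label trial, awareness of allocation at week 12 has to be accepted; at baseline it need not be.

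**Working it through.** **1. The sequence, from the text**

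| Step | Where stated |
|---|---|
| Consent signed, then code generated; no questionnaire mentioned between | Randomization |
| Registration, account activation, download and login, all after randomisation | Intervention (LuCApp) |
| LuCApp-arm questionnaires collected in the app | Participants |
| FACT-L via LuCApp, with baseline named among the time points | Sample size |

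The first two rows give the order and the last two give the mode. Combined, they put the LuCApp baseline after allocation. The only other anchor, that randomisation precedes medical therapy, does not place baseline before randomisation.

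**2. The plan's own figure**

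Inputs from Sample size: difference 6, SD 11.54, 80% power, two-sided alpha 0.05, 120 patients.

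Normal formula: n per arm = 2 × (11.54/6)² × (1.960 + 0.842)² = 58.07, so 59 per arm, 118 in all. The t-based solution is 59.05, so 60 per arm, 120 in all. The stated 120 is reproduced. Power at 60 per arm is 80.6% (t-based).

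**3. How a baseline shift enters the result**

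Let b be an assumed net shift in mean TOI at baseline in the LuCApp arm, and p the fraction still present at week 12.

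- Baseline after allocation: bias in the change score = pb − b, of size (1 − p)b.
- Baseline before allocation: bias = pb.

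**4. Illustration with p = 0**

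SE = 11.54 × √(2/60) = 2.107, df 118, noncentral t. The values of b are assumptions; the documents give none.

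| b (TOI points) | False-positive rate | Power for a true 6, shift against LuCApp | Power, shift favouring LuCApp |
|---|---|---|---|
| 0 | 5.0% | 80.6% | 80.6% |
| 1 | 7.6% | 65.3% | 90.9% |
| 2 | 15.6% | 46.9% | 96.5% |
| 3 | 29.2% | 29.2% | 98.9% |

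**5. Why these are not the gain from moving the baseline (b = 2)**

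| p | False-positive rate, as written | False-positive rate, baseline before allocation |
|---|---|---|
| 0 | 15.6% | 5.0% |
| 0.25 | 10.9% | 5.6% |
| 0.5 | 7.6% | 7.6% |
| 0.75 | 5.6% | 10.9% |
| 1 | 5.0% | 15.6% |

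On this one bias, moving the baseline gives the smaller error only if p is below 0.5. What remains after the move is the open-label bias at week 12.

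**6. The same algebra applied to mode**

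If baseline moves to paper and later LuCApp questionnaires stay in the app, a constant paper-to-app offset m no longer cancels within that arm and passes in full into the between-arm difference. An assumed m of 1 or 2 points gives the same 7.6% or 15.6% as in step 4.

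**The case against.** The strongest objection is that the order of baseline and randomisation would naturally be shown in Figure 1 (recruitment, randomisation and data collection) and Figure 6 (assessment time points), and neither can be read here. The Sample size sentence is mainly about mode, and the Randomization section gives order, not immediacy. A reader might infer that the trial certainly takes its baseline after allocation in both arms. The documents do not support that: for control patients the text is silent, and for LuCApp patients the figures may say otherwise. What stands is that the text, followed as written, gives a post-allocation LuCApp baseline. If the figures differ, the two must be reconciled.

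Second, the shifts illustrated may be generous: 2 to 3 points is a third to a half of the 6-point target. TOI omits the emotional and social subscales, early contact is a 15-minute presentation and a short tip, and therapy has not begun. This is fair. It limits any claim about size, but not the principle.

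Third, a paper baseline changes mode in one arm only. This also stands. The FACT-L paragraph under Outcomes acknowledges small differences by mode but regards the formats as essentially equivalent at group level. That supports accepting the switch, without proving the offset is zero. It does not address answers given with allocation known.

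Finally, the trial calls itself a feasibility study and a pilot. It nevertheless has a powered primary comparison at two-sided 0.05.

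**Conclusion.** The point holds as a gap in the stated sequence that should be closed before enrolment. Read together, the Participants, Intervention (LuCApp), Sample size and Randomization sections have LuCApp patients answer baseline in an app they receive after randomisation, and nothing readable places baseline before allocation in either arm. This exposes the primary change score to an avoidable influence.

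Neither size nor direction can be derived from the documents. The error rates above rest on assumed shifts, SD 11.54 and 60 analysed per arm. A reader might take 15.6% or 29.2% as the trial's actual false-positive rate, or as what the fix recovers; neither reading is supported, because b, p and m are all unknown. The case for moving the baseline is one of principle: a baseline taken before allocation cannot be affected by it, and the plan should not rely on an affected baseline happening to cancel open-label bias at week 12. Confidence is medium because the two figures are unseen.

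**What to change.** 1. State that every patient completes baseline FACT-L, EQ-5D-5L and HADS after consent and before the randomisation code is generated, in the same mode in both arms (for example, paper). The wording is needed in Participants, in Intervention (LuCApp) both where the order of steps is described and under the Questionnaires component, in Sample size, and in Randomization. Changing only some of these would leave the text contradicting itself.
2. Record the completion date, and the time, of each baseline questionnaire relative to randomisation.
3. Check Figures 1 and 6 and bring text and figures into agreement.
4. Later questionnaires may stay in the app for the LuCApp arm. If baseline is on paper, state as a limitation that this arm changes mode once and that any paper-to-app offset enters the between-arm difference.

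Cost: wording in five places, a date and time field, and, if paper is used, one pack with data entry for each LuCApp patient (156/2 = 78). Sample size and later in-app collection do not change. No extra visit should be needed, since Intervention (LuCApp) puts consent and randomisation in hospital before therapy. However, Ethics & Informed Consent has patients send the signed form to the team, which may imply signing elsewhere, so the place of consent should be confirmed at the same time.
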